#### **4.5. Sample size calculation**

The sample size calculation is based on demonstrating non-inferiority between the detection rate of clinically significant cancer from the PCaVision pathway and the MRI pathway using patients as the unit of analysis and data from the fully paired design.

The detection rates of PCa (GG $\geq$ 2) based on MRI and PCaVision targeted biopsies are expected to be around 30%. These values are based on the detection rates of PCa (GG $\geq$ 2) reported by Mannaerts et al., 2020 [30] and Grey et al., 2022 [43], which were found to be 29% and 30% with MRI and 28% and 26% with 2D CUDI (older version of PCaVision), respectively.

The non-inferiority margin is set to 5% absolute difference in detection rate. The expected proportion of discordant pairs is 10%. This proportion expresses the degree in which PCaVision and MRI disagree with respect to detecting and missing significant cancers in a paired design. This parameter is relevant when analysing data from a paired study design. A smaller percentage of discordant pairs will lower the required sample size. In the studies of Mannaerts et al., 2020 [30] and Grey et al., 2022 [43], the percentage discordant pairs were 10.1% and 8.9%, respectively.

Our assumptions of the sample size calculations are therefore the following: an expected detection rate of 30% for both imaging techniques, a non-inferiority margin of 5% points and a percentage discordance between both imaging techniques of 10%, a one-sided type 1 error of 2.5% (as recommended by the European Medicines Agency) and a power of 80%. This leads to a required total sample size of 350 patients.. This is the total number of men who need to undergo both PCaVision and MRI, and produce images of sufficient quality, followed by targeted biopsies if indicated. This sample size calculation was performed according to Liu et al., 2002 [47] and Hintze, 2008 [48].

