### 10.1. Primary study endpoint analysis

The main analysis is the comparison of the detection rate of clinically significant cancer (defined as GG $\geq$ 2) between the PCaVision targeted biopsy pathway and the MRI targeted pathway. We will calculate the difference in these detection rates and its corresponding 97.5% confidence interval. Because of the paired design of our study, we will use the approach of Liu which accounts for the correlation between the detection rates of both pathways [44,45,46]. A one-sided 2.5% equivalence test will be performed to formally evaluate whether the lower bound of the confidence interval will not exceed the non-inferiority margin specified at an absolute difference in detection rates of 5%.

As a secondary analysis, the comparison of the proportion of men in whom targeted biopsies could have been safely omitted in the PCaVision pathway compared to the MRI pathway.

This ~~10.2. Secondary study endpoint analysis~~ with respect to detection rate (see above) does not come at the price of fewer patients in whom targeted biopsies can be prevented (e.g., more unnecessary targeted biopsies). For PCaVision this proportion is the number of men in whom there are no lesions to be biopsied based on PCaVision while the MRI biopsy strategy and systematic biopsy (when performed) did not detect clinically significant cancer divided by the total number of men in the study. Likewise, this proportion for MRI is defined as the number of men in whom there are no lesions to be biopsied based on MRI while the PCaVision biopsy strategy and systematic biopsy (when performed) did not

detect clinically significant cancer divided by the total number of men in the study. Given the fully paired nature of the design, the proportions will be tested for being statistically significance different using the McNemar test (two-sided alpha of 5%). The approach of Liu which accounts for the correlation [44,45,46] will be used to calculate a 95% confidence interval for the difference between these proportions.

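### The safe-omission comparison aims to show no loss of avoided biopsies, but its only test is a two-sided McNemar test of difference, and the planned confidence interval has no margin or reading rule

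*Combined protocol and SAP*

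**What the plan says.** The safe-omission analysis is described where sections 10.1 and 10.2 meet; in the available text the 10.2 heading falls inside the sentence that gives its purpose. What survives of that sentence says the result on detection rate "does not come at the price of fewer patients in whom targeted biopsies can be prevented". The next steps are:

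- **Measure.** For each pathway, count the men with no lesion to biopsy in whom the other pathway and any systematic biopsy found no clinically significant cancer, "divided by the total number of men in the study".
- **Test.** "the proportions will be tested for being statistically significance different using the McNemar test (two-sided alpha of 5"%).
- **Interval.** The paired approach of Liu "will be used to calculate a 95% confidence interval for the difference between these proportions".

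No margin, expected difference, discordance or power is given for this endpoint, and no rule says how a non-significant test or the interval is to be read. The planning values in section 4.5 concern detection only: "The non-inferiority margin is set to 5% absolute difference in detection rate" and "The expected proportion of discordant pairs is 10"%. The Summary and sections 2 and 8.1.2 describe the safe-omission aim simply as a comparison.

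**The concern.** The purpose, as far as it can be read, is a not-worse-than statement. To support it, the data must exclude a loss of some stated size. A McNemar test starts from equality and asks whether the data contradict it. Failing to contradict equality is what one sees when there is no loss, but also when there is a loss and too few discordant pairs to show it. The plan uses the right form for detection, where a confidence bound is read against a margin, but not here.

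Safe omission is the first secondary objective and the plan's stated counterweight to the primary claim. A technique that calls more men positive tends to find more cancer and to spare fewer men a biopsy, so non-inferior detection is hard to interpret without knowing what happened to avoided biopsies. If the report leaned on a non-significant p-value for this, the conclusion would have no statistical support.

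**Working it through.** **Step 1: reproduce the plan's own figure.** Inputs from section 4.5: margin 0.05, discordance 0.10, equal detection rates, "a one-sided type 1 error of 2.5% (as recommended by the European Medicines Agency) and a power of 80"%. The score form uses the restricted null estimates of the two discordant cells, 0.0345 and 0.0845, so the null variance per pair is 0.1189 − 0.05² = 0.1164.

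n = [(1.960 × √0.1164 + 0.8416 × √0.10) / 0.05]² = 349.6, rounded up to 350.

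This matches: "This leads to a required total sample size of 350 patients". The simple Wald form gives 7.849 × 0.10 / 0.05² = 314, so the score form is the one that fits. Inflating, 350 × 1.25 = 437.5, hence 438.

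**Step 2: McNemar test on safe omission.** Let ψ be the discordance in safe omission and δ the true loss (MRI minus PCaVision). The proportion of men spared by MRI only is (ψ + δ)/2, and by PCaVision only (ψ − δ)/2. The test flags the loss when (MRI-only − PCaVision-only)/√(discordant pairs) exceeds 1.96. Approximately,

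power = Φ[(δ√n − 1.96√ψ) / √(ψ − δ²)].

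For n = 350, ψ = 0.20, δ = 0.05: (0.935 − 0.877)/0.444 = 0.13, so power is about 55%. Full enumeration of the discordant counts gives 55.8%, so 44% of such trials would be non-significant. The table uses enumeration. Both 350 and 438 are shown because the denominator can be read as the paired set or as all men.

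| Assumed discordance | 5-point loss missed, n = 350 | 3-point loss missed, n = 350 | 5-point loss missed, n = 438 | 95% CI half-width, n = 350 |
|---|---|---|---|---|
| 10% | 14% | 57% | 7% | 3.3 points |
| 15% | 32% | 70% | 22% | 4.1 points |
| 20% | 44% | 76% | 35% | 4.7 points |
| 30% | 60% | 83% | 52% | 5.7 points |
| 40% | 69% | 86% | 62% | 6.6 points |

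The exact McNemar test misses slightly more (18% instead of 14% in the first cell). Five points is 17.5 of 350 men or about 22 of 438.

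**Step 3: how plausible is the range?** It is an assumption. The 10% is the planning value for detection, a different outcome. A guide for safe omission comes from the MRI specificity of 0.37 and 30% prevalence in section 1, treating men with no significant cancer found as men without it:

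- MRI safe omission: 0.7 × 0.37 = 0.259.
- With a 5-point loss, PCaVision: 0.209, a specificity of 0.209/0.7 = 0.30.
- If the two calls were independent in cancer-free men: ψ = 0.7 × (0.37 × 0.70 + 0.30 × 0.63) = 0.31.

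Positive correlation lowers this. With equal specificities of 0.37, ψ = 0.7 × 2 × 0.37 × 0.63 × (1 − ρ) = 0.326 × (1 − ρ), so 10% needs ρ of about 0.69 and 20% about 0.39. The low end therefore requires strong agreement between the techniques; 40% lies above what independence gives here.

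**Step 4: what a margin-based reading would do.** Take a 5-point tolerance for illustration only (the documents set none for this endpoint), the score test and n = 350. The chance of wrongly claiming no price at a true 5-point loss is 2.3% to 2.5% at every discordance tried. The chance of making the claim when there is no loss is 81%, 54%, 40% and 31% at discordances of 10%, 20%, 30% and 40%. For 80% power the Wald form, 7.849 × ψ / 0.05², gives 314, 628, 942 and 1,256 men.

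**The case against.** The strongest reply is that the objective is stated elsewhere only as a comparison, for which a two-sided test with an interval is adequate; that the purpose sentence is damaged and its lost opening may have been mere motivation; and that the planned interval would show any loss. Much of this stands, and it rules out several stronger readings.

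- A reader might infer that a real loss will often be read as no price. The documents do not say that non-significance will be read that way, and how often a loss is missed turns on a discordance they do not give. At 10%, a 5-point loss would be flagged in about 86% of trials with 350 men and 93% with 438.
- A reader might infer that this is the plan's only check on over-calling. It is not: detection of ISUP 1 cancer is compared, and histology by pathway is cross-tabulated from no cancer to Grade Group 5. The limit of two lesions and six cores per technique also restricts any gain from marking more lesions.
- A reader might combine the specificities 0.37 (MRI) and 0.55 (2D CUDI) to get a discordance of 36%. Those values make PCaVision spare 0.7 × (0.55 − 0.37) = 12.6 points more men than MRI, which is not a loss scenario. The 0.55 also comes from a localisation study against prostatectomy specimens, so it is unlikely to be a patient-level specificity in men without significant cancer.

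What the reply does not remove is the gap between aim and tool. The surviving words state a no-loss aim, the only test attached cannot support it, and nothing says how the interval is to be used.

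**Conclusion.** The point holds as one of inference, whatever the discordance: a non-significant two-sided McNemar test cannot support the statement that detection was not bought with fewer avoided biopsies, and the interval that could address the question has no margin or reading rule.

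Its practical size is uncertain because it depends on the assumed discordance. Over the whole range in the table the McNemar test could miss a 5-point loss seldom or in most trials; a 3-point loss would be missed in more than half of trials with 350 men even at the lowest value. The finding concerns a secondary endpoint and leaves the primary analysis untouched. It does not show that the sponsor intends to misread the test, only that the plan does not prevent it.

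**What to change.** In section 10.2, restore the damaged purpose sentence and add three statements:

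1. Any conclusion about the price in avoided biopsies rests on the estimated paired difference (PCaVision minus MRI) and its planned 95% confidence interval.
2. A non-significant McNemar test is not evidence of no loss.
3. The McNemar test is used only to claim a difference.

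Optionally, if the sponsor wants a formal no-price claim, fix and justify a tolerance for safe omission before database lock and require the lower confidence limit to lie above it. The 5 points set for detection should not be carried over without a reason specific to avoided biopsies.

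The first part costs one paragraph and no new data, though the statement on avoided biopsies may be less favourable. The optional part costs more: as step 4 shows, at discordances of 20% or more an equally good technique would make a 5-point claim only about half the time or less with 350 men. The sponsor should know before choosing this route that the claim may be out of reach at the planned size.

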## SUMMARY

### Rationale:

The incidence of prostate cancer (PCa) has increased over the years. To diagnose a patient with PCa, histopathological confirmation is required. Different diagnostic pathways are currently available. Systematic biopsies have long been the cornerstone in the diagnostic work-up of men suspected for prostate cancer. Systematic biopsies, however, can lead to under-diagnosing of clinically significant prostate cancer (csPCa) and each biopsy is associated with the risk of infection and other side effects.

In the magnetic resonance imaging (MRI) pathway, targeted biopsies are only performed when suspicious lesions are detected on MRI. The MRI pathway purposely detects fewer clinically insignificant prostate cancer (ciPCa), but has an increased sensitivity for csPCa, and an increased localization accuracy of cancer suspicious regions. The MRI-based strategy is now recommended as the first-line investigation. However, reported sensitivities and specificities for MRI vary widely between studies which can be attributed to a difference in MRI equipment, study design related to the quality of reference standard procedure, and inter-observer variability. Moreover, MRI suffers from limited availability, and is a time-consuming and expensive imaging modality.

Transrectal ultrasound, which is widely available, cheaper to implement and familiar to the urologist could be a valid alternative. In an ultrasound pathway, 2D contrast-enhanced ultrasound (CEUS) in combination with contrast-US-dispersion imaging (CUDI) focuses on the detection of angiogenetic changes in the microvascular architecture, to localize lesions suspected for PCa, followed by target biopsies for histological confirmation. Promising results for 2D CEUS have been obtained and it is expected that 3D multiparametric ultrasound (mpUS) including 3D CUDI will allow more accurate identification of significant prostate cancer.

PCaVision software was developed for post-processing analysis of several modalities of ultrasound data of the prostate including 3D CEUS. PCaVision combines Image Analysis Software and Viewing Software developed as an algorithm based on machine learning trained in the detection of lesions suspect for cancer.

The overall aim of this study is to compare the diagnostic accuracy of two different diagnostic pathways to detect csPCa in biopsy-naïve men: (1) PCaVision targeted biopsy pathway; (2)

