### **Objective:**

The primary objective is to demonstrate non-inferiority of the detection rate of clinically significant prostate cancer in targeted biopsies based on PCaVision imaging (PCaVision pathway) in comparison with the detection rate of clinically significant cancer in targeted biopsies based on MRI (MRI pathway). In this comparison, clinically significant prostate cancer is defined as International Society of Urological Pathology (ISUP) Grade Group (GG)  $\geq 2$  in any of the biopsy cores taken from a lesion.

Secondary objectives are (1) to compare the proportion of men in whom targeted biopsies could be “safely” omitted in the PCaVision pathway, defined as the number of men in whom no lesions for target biopsies have been identified by PCaVision while no clinically significant cancer is detected in either MRI targeted biopsies or possible systematic biopsies, compared to the MRI pathway, (2) to perform the same diagnostic assessments described in the Primary objective for different definitions of the target condition, including (i) ISUP  $\geq 3$  in any of the biopsy cores taken from a lesion; (ii) ISUP  $\geq 2$  with cribriform growth and/or intraductal carcinoma (CR/IDC) in any of the biopsy cores taken from a lesion; (iii) ISUP = 1, (3) to compare the number of men in whom the PCaVision pathway provided insufficient quality images with the number of men with insufficient quality MRI images

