### Secondary Objectives

- To compare the proportion of men in whom targeted biopsies could be safely omitted in the PCaVision pathway versus the MRI pathway. This is defined as the number of men in whom no lesions for target biopsies have been identified by PCaVision while no clinically significant cancer is detected in either MRI targeted biopsies or systematic biopsies. The combined findings of all types of biopsies will serve as the reference standard to define 'safe'.
- To perform the same diagnostic accuracy analyses as described in the primary objectives for different definitions of the target condition. This includes: (i)  $ISUP \geq 3$  in any of the biopsy cores taken from a lesion; (ii)  $ISUP \geq 2$  with cribriform growth and/or intraductal carcinoma (CR/IDC) in any of the biopsy cores taken from a lesion; (iii)  $ISUP = 1$ .
- To compare the number of men in whom the PCaVision pathway generated insufficient quality images with the number of men with insufficient quality MRI images in the MRI pathway.
- To perform the same diagnostic accuracy analyses as described in the primary and secondary outcome with different levels of increased criteria for ultrasound image quality, automatically detected by PCaVision

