#### 8.1.2 Secondary study parameters/endpoints

- proportion of men in whom targeted biopsies could have been safely omitted in the PCaVision pathway compared to the MRI pathway. This is defined as the number of men in whom no lesions for target biopsies have been identified by PCaVision while no clinically significant cancer is detected in either MRI targeted biopsies or systematic biopsies. The combined findings of all types of biopsies will serve as the reference standard to define 'safe'.
- same diagnostic accuracy analyses as described in the primary endpoint for different definitions of the target condition. This includes: (i) ISUP  $\geq 3$  in any of the biopsy cores taken from a lesion; (ii) ISUP  $\geq 2$  with cribriform growth and/or intraductal carcinoma (CR/IDC) in any of the biopsy cores taken from a lesion; (iii) ISUP = 1.
- comparison of the number of men in whom the PCaVision pathway provided insufficient quality images or targeted biopsies with the number of men with insufficient quality MRI images or target biopsies in the MRI pathway.
- same diagnostic accuracy analysis as described in the primary and secondary outcome but using increased ultrasound image quality requirements (predefined and automated in PCaVision)

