### **8.3.3 Biopsy procedure and histological examination**

An urologist will perform software-assisted fusion TBx or cognitive TBx based on the standard of care of each participating centre. For each imaging modality (e.g. MRI and 3D mpUS), a maximum of 2 lesion will be targeted. Each lesion will be sampled using 3 biopsy cores. In case both imaging techniques have identified lesions to be biopsied, the targeted biopsy procedures are performed in a randomized order to prevent potential bias.

The applied prostate biopsy method; transperineal will be selected based on the standard of care of each participating clinical centre.

Individual biopsy cores from targeted biopsies will be separately analysed by an uropathologist for the presence of PCa, ISUP, Gleason score (GS), percentage tumour core involvement and morphological patterns including cribriform growth pattern and intraductal carcinoma (CR/IDC) in accordance with the 2019 ISUP guidelines [34]. A work order instruction for the exact sample labelling of the biopsies and histopathological workup will be provided and agreed on with each clinical site.

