Furthermore, the same effect measures and statistical approach will be used as in the previous analyses, only the definition of the target condition will change. The following alternative definitions of the target condition (rather than  $ISUP \geq 2$ ) will be used: (i)  $ISUP \geq 3$ ; (ii)  $ISUP \geq 1$ ; (iii)  $ISUP = 1$ . The reason also assessing alternative definitions is that there is still ongoing discussion about the clinical relevance of these histological findings.

Both imaging techniques (PCaVision and MRI) can produce images of insufficient quality impeding the process of taking targeted biopsies. This hampers the clinical usefulness of the imaging technique in practice. Therefore, we will compare the proportion of men in whom the PCaVision pathway produces insufficient-quality images or targeted biopsies with the proportion of men with insufficient-quality MRI images or target biopsies in the MRI pathway. The same statistical approach for paired proportions will be used in the comparison of the detection rate.

The PCaVision software includes automated detection of ultrasound image quality by analysing patient motion and CEUS signal. We will analyse diagnostic accuracy of PCaVision using the same statistical approach with increased requirements of ultrasound images quality with regards to motion and CEUS signal. The exact levels of these increased requirements are described in section 6.1.2.

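### Section 10.2 analyses ISUP ≥1 in place of the stated endpoint ISUP ≥2 with CR/IDC, and leaves open whether ISUP = 1 gets the primary lower-bound non-inferiority test

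*Combined protocol and SAP*

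**What the plan says.** Three places in the protocol give the same list of alternative target conditions: the Summary (Objective), Section 2 (Secondary Objectives) and Section 8.1.2. The list is ISUP ≥3; ISUP ≥2 "with cribriform growth and/or intraductal carcinoma (CR/IDC) in any of the biopsy cores taken from a lesion"; and ISUP = 1. All three tie the analysis to the primary one; Section 2, for example, says "To perform the same diagnostic accuracy analyses as described in the primary objectives for different definitions of the target condition". Section 8.3.3 has the pathologist report cribriform growth and intraductal carcinoma for each targeted core.

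Section 10.2, whose heading is run into the text in the available copy, gives a different list: ISUP ≥3, ISUP ≥1 and ISUP = 1. On method it says only that "the same effect measures and statistical approach will be used as in the previous analyses, only the definition of the target condition will change".

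Two analyses come before that sentence in chapter 10:

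- The primary analysis is a one-sided 2.5% test of "whether the lower bound of the confidence interval will not exceed the non-inferiority margin specified at an absolute difference in detection rates of 5" per cent.
- The analysis of safely omitted biopsies compares proportions that are "tested for being statistically significance different using the McNemar test (two-sided alpha of 5" per cent), with a 95% interval for the paired difference.

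On the direction of benefit, the Summary (Rationale) says: "The MRI pathway purposely detects fewer clinically insignificant prostate cancer (ciPCa"). Section 1 likewise counts reduced detection of Grade Group 1 disease among the gains of MRI-targeted biopsy over systematic biopsy. No section gives a margin, a direction or a named test for ISUP = 1.

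**The concern.** There are two separate problems.

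The first is which conditions are analysed. A statistician programming from chapter 10 would produce an any-cancer comparison (ISUP ≥1) that is neither an objective nor an endpoint, and would produce nothing for ISUP ≥2 with CR/IDC, which is both. One cannot be shorthand for the other: ISUP ≥1 adds insignificant disease to significant disease, whereas the CR/IDC condition is a subset of significant disease. With two lists in force, the choice of which to report could be made after the results are known.

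The second is how ISUP = 1 is tested. A lower-bound non-inferiority test asks whether PCaVision finds not too many fewer cases than MRI. That suits cancers one wants to find. For ISUP = 1 the protocol's own rationale points the other way, so the carried-over test would be passed most easily when PCaVision finds more insignificant cancer. A real reduction of 5 points or more would almost always fail it.

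**Working it through.** **Lists side by side**

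| | Summary, Section 2, Section 8.1.2 | Section 10.2 |
|---|---|---|
| (i) | ISUP ≥3 | ISUP ≥3 |
| (ii) | ISUP ≥2 with CR/IDC | ISUP ≥1 |
| (iii) | ISUP = 1 | ISUP = 1 |

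Items (i) and (iii) agree. Item (ii) is legible in all four places and differs.

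**Which test applies to ISUP = 1.** Section 10.2 refers to previous analyses in the plural, which can cover both the lower-bound test and the McNemar comparison. The Summary, Section 2 and Section 8.1.2 refer to the primary analysis alone. Read together, the documents lean towards the lower-bound test without saying so.

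**The plan's sample size.** Section 4.5 gives discordance 0.10, margin 0.05, one-sided alpha 0.025, power 80% and equal detection rates. With the restricted maximum-likelihood variance at the margin, v₀ = 0.1164:

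n = (1.960·√0.1164 + 0.8416·√0.10)² / 0.05² = (0.6687 + 0.2661)² / 0.0025 ≈ 349.6, so 350.

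This agrees with the plan, and 350 × 1.25 = 437.5 gives its total of 438. The figure of 350 evaluable men is used below.

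**Illustration for ISUP = 1.** The documents give neither the ISUP = 1 discordance (ψ) nor the ISUP = 1 difference (d, PCaVision minus MRI). Both are assumed here: ψ from 0.06 to 0.15 and d = ±0.05. The 10% in Section 4.5 is for GG ≥2.

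The probability of passing the lower-bound test, by normal approximation, is

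P = Φ[(d + 0.05)·√350 / √(ψ − d²) − 1.96].

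- At d = +0.05 and ψ = 0.15: 0.10 × 18.708 / √0.1475 − 1.96 = 4.871 − 1.96 = 2.911, so P = 0.998. At ψ = 0.06 and ψ = 0.10, P = 1.000.
- At d = −0.05 the first term is zero, so P = Φ(−1.96) = 0.025 at every ψ.

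Exact enumeration over the discordant pairs, using the paired score test and an uncorrected two-sided McNemar test, gives:

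| ψ | Lower-bound test passed, d = +5 points | Lower-bound test passed, d = −5 points | McNemar significantly lower, d = −5 points |
|---|---|---|---|
| 0.06 | 1.000 | 0.019 | 0.991 |
| 0.10 | 1.000 | 0.023 | 0.865 |
| 0.15 | 0.998 | 0.024 | 0.684 |

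The ψ = 0.06 row is an extreme case. A 5-point reduction then needs a split of 5.5% against 0.5%, so 0.055/0.06 = 92% of discordant men fall one way.

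**The case against.** The list mismatch is hard to dispute, but its harm is limited. Three sections agree, CR/IDC is recorded per core, and the missing analysis could be run at any time. It is one item in a secondary analysis.

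On ISUP = 1 the other side has more to say. The plan nowhere defines success for ISUP = 1. The 5-point margin is stated only for significant cancer, and Section 10.2 does not repeat it; the reason given there, continuing debate over clinical relevance, reads as exploratory. On either reading the paired difference and its interval would be reported, so an excess of ISUP = 1 would be visible, as it would in the planned cross-tabulation by grade group. The direction of benefit is inferred from statements about MRI, in Section 1 against systematic biopsy, and not from a statement about PCaVision against MRI. Finally, the 2% figure is simply the test's alpha at its own margin, and the near-100% figure follows from lying 10 points above that margin.

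Most of this stands as a limit on weight. The estimate and interval would protect a careful reader, and the probabilities show how the test behaves without predicting anything about this trial. It does not remove the problem. The two lists still conflict, the formal conclusion for ISUP = 1 is still unspecified, and the reading best supported by the text runs against the protocol's rationale. The cross-tabulation is by grade group and would not show CR/IDC.

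**Conclusion.** The concern holds. The conflict between Section 10.2 and the three other places rests on the text alone and needs no assumption. Followed as written, 10.2 omits a named endpoint and analyses a condition that is not one.

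For ISUP = 1 the conclusion is conditional. If the primary test is carried over, its formal result points the wrong way; if the two-sided comparison is meant, it does not. The documents do not say which. The direction of the problem does not depend on the assumed discordance; only the probabilities do. The point should be corrected, but it is confined to secondary analyses: the primary test, the 350 evaluable men and the total of 438 are unchanged.

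**What to change.** 1. Make the list in Section 10.2 the same as in Section 8.1.2: ISUP ≥3; ISUP ≥2 with CR/IDC; ISUP = 1. The sponsor should confirm that this is the intended list.
2. Keep ISUP ≥1 only if it is also added to the objectives and endpoints. It contains ISUP = 1, so its test and direction would then need stating too.
3. For ISUP = 1, specify the paired difference with a two-sided 95% interval and the McNemar test already used in chapter 10. State that lower is better and that no lower-bound non-inferiority claim will be made. The paired difference and interval without a test would also be acceptable.
4. For each remaining target condition, name the test rather than refer to previous analyses.

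The change should be made and dated before results are known. It needs no new data, patients or methods. The cost is that there would be no formal non-inferiority statement for ISUP = 1, and that at the top of the assumed discordance range (15%) the McNemar test has only about 68% power for a 5-point reduction.

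### On its plain reading, section 10.2 carries safe omission over to the target condition ISUP = 1, where the measure is inverted; the objectives and endpoints repeat only the detection-rate analysis

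*Combined protocol and SAP*

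**What the plan says.** Section 10.1 sets out the primary analysis: "The main analysis is the comparison of the detection rate of clinically significant cancer" (GG ≥2) between the two targeted-biopsy pathways. The secondary analysis text then introduces a second measure: "As a secondary analysis, the comparison of the proportion of men in whom targeted biopsies could have been safely omitted" under PCaVision, compared with MRI. For PCaVision the numerator equals "the number of men in whom there are no lesions to be biopsied based on PCaVision while the MRI biopsy strategy and systematic biopsy", if taken, found no clinically significant cancer. The MRI numerator mirrors this. Both are divided by all men in the study, compared with a McNemar test, and given a Liu-type interval for the difference.

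The next paragraph turns to other target conditions and says that "the same effect measures and statistical approach will be used as in the previous analyses, only the definition of the target condition will change". It then lists ISUP ≥3, ISUP ≥1 and ISUP = 1 as replacements for ISUP ≥2.

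The places that define what is to be estimated are narrower. Section 2 reads: "To perform the same diagnostic accuracy analyses as described in the primary objectives for different definitions of the target condition". Section 8.1.2 lists the "same diagnostic accuracy analyses as described in the primary endpoint for different definitions of the target condition". The objective paragraph of the summary also ties the alternative definitions to the primary objective. For the stricter image-quality criteria, by contrast, sections 2 and 8.1.2 name the primary and the secondary outcome together.

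**The concern.** There are two linked problems. The first is scope: section 10.2 is broader than the objectives and endpoints that it implements. The second is what the broader scope produces. Safe omission asks whether the biopsies outside the index pathway failed to find the target condition. That works when the target is a threshold such as ISUP ≥2. It does not work when the target is one exact grade at the bottom of the scale, because every higher grade then fails to meet the target.

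The plan includes safe omission to show that detection performance is not bought with more unnecessary biopsies. With ISUP = 1 substituted, the count would credit a pathway for significant cancers that it left unmarked and debit it for sparing men an ISUP 1 diagnosis, under a label that says safe.

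**Working it through.** **Step 1. Scope, side by side.**

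| Place | What is repeated under other target conditions |
|---|---|
| Summary, objective | Primary objective |
| Section 2, secondary objectives | Primary objective |
| Section 8.1.2 | Primary endpoint |
| Section 10.2 | Effect measures of the preceding analyses, not itemised |

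Two analyses precede the sentence in section 10.2: the detection rate and, immediately before it, safe omission. Nothing there excludes the second.

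**Step 2. Substituting each target condition into the safe-omission definition.** Take a man with no PCaVision lesion. The rows give what his MRI-targeted or systematic cores show. The cells say whether he counts as safely omitted.

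| Cores show | ISUP ≥2 | ISUP ≥3 | ISUP ≥1 | ISUP = 1 (highest grade) | ISUP = 1 (any core) |
|---|---|---|---|---|---|
| No cancer | safe | safe | safe | safe | safe |
| Only ISUP 1 | safe | safe | not safe | not safe | not safe |
| Only ISUP 2 | not safe | safe | not safe | safe | safe |
| Only ISUP 4 | not safe | not safe | not safe | safe | safe |
| ISUP 1 and ISUP 2 | not safe | safe | not safe | safe | not safe |
| ISUP 1 and ISUP 4 | not safe | not safe | not safe | safe | not safe |

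ISUP ≥3 lets a missed ISUP 2 through, but that is what choosing a higher threshold means. ISUP ≥1 lets no detected cancer through. Only ISUP = 1 lets every higher grade through. For men with only higher-grade cores this holds on both readings of ISUP = 1. For men with mixed grades it holds only if ISUP = 1 means highest grade, which the plan does not say.

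**Step 3. Size, from the plan's inputs (section 4.5).** The inputs are a detection rate of 30% in both pathways, discordance of 10%, a margin of 5 points, one-sided alpha of 2.5%, power of 80% and 350 evaluable men. They reproduce the stated sample size. With the score-test variance for paired proportions (v0 = 0.1164 at the margin, v1 = 0.10 under equal rates),

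N = [(1.960·√0.1164 + 0.842·√0.10) / 0.05]² = 349.6, i.e. 350.

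Equal rates split the discordance evenly, so ISUP ≥2 found by MRI-targeted biopsy only is 10% / 2 = 5% of men, or 0.05 × 350 = 17.5 men. A man with no PCaVision lesion has no PCaVision cores, so every such man with ISUP ≥2 in MRI cores lies in this 5%. Let s be the share of the 5% with no PCaVision lesion. The plan does not give s, so the full range is shown, counting every such man as reclassified:

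| s | Men moved to safe (17.5 × s) | Percentage points (5 × s) |
|---|---|---|
| 0% | 0 | 0 |
| 25% | 4.4 | 1.25 |
| 50% | 8.75 | 2.5 |
| 75% | 13.1 | 3.75 |
| 100% | 17.5 | 5 |

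Under the any-core reading fewer men move, but the range stays 0 to 17.5. The same calculation applies to MRI with its own share. The net contribution to the difference is therefore 5 × (s for PCaVision − s for MRI) points. It is zero if the shares are equal and at most 5 points either way.

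Two movements are left out because the plan gives no rate for them: ISUP ≥2 found only by systematic biopsy, which adds to the count, and men with only ISUP 1, who move from safe to unsafe.

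**The case against.** The strongest reply is that the authors meant detection rates only. Section 10.2 does not itemise the earlier analyses. The summary and sections 2 and 8.1.2 all limit the repeat to the primary analysis. Sections 2 and 8.1.2 also mention secondary outcomes explicitly where they are wanted. Every definition of safe omission is worded in terms of clinically significant cancer, which the plan defines as GG ≥2, and ISUP 1 is treated as insignificant. Section 10 also promises a cross-tabulation of grades by pathway, so cancers missed on targeted biopsy would be visible to a careful reader.

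Much of this stands. The intention may well have been narrower, and the effect is confined to one secondary analysis. It does not settle the matter, because section 10.2 is where the calculation is specified. It refers to effect measures and analyses in the plural, directly after safe omission, and says that only the target condition changes.

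Two stronger readings should be resisted. A reader might infer that the plan declares a missed significant cancer to be a safe omission. No sentence says so: the result requires the repeat to include safe omission, and the new target condition to replace clinically significant cancer in its definition. A reader might also infer that the McNemar test would come out significant in favour of the worse pathway. The documents do not support that. The test depends on all the other discordant men, whose numbers are not given, and men added equally on both sides weaken it. The plan assumes equal detection rates, and a large gap in missed cancers would show in the primary comparison against its 5-point margin. No p-value can be quoted.

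**Conclusion.** The point holds as a defect of scope and definition in a secondary analysis. On the plain reading of section 10.2, safe omission is computed for ISUP = 1 and is inverted there. In men without mixed grades, this follows from the definition and needs no numerical assumption.

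The size is 0 to 17.5 of 350 men, or 0 to 5 percentage points, per pathway. It rests on the plan's 10% discordance and equal rates, on an unstated share of men with no lesion marked, and on the 350 evaluable men as denominator. Over all 438 enrolled men the upper end would be 17.5 / 438 = 4.0 points. The effect partly cancels in the difference between pathways when miss rates are equal. The primary test, its alpha and the sample size do not change.

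**What to change.** Replace the scope sentence in section 10.2 with wording such as: *For the alternative target conditions, the detection-rate comparison of section 10.1 is repeated. Safe omission is evaluated only against a threshold for significant cancer (ISUP ≥2, and ISUP ≥3 if wanted) and is not computed for ISUP = 1.* This matches the summary and sections 2 and 8.1.2. State as well whether ISUP = 1 means highest grade or any core, since the detection-rate comparison needs that too.

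If the number of men spared an ISUP 1 diagnosis is of interest, report it separately under its own name: men with no index lesion, ISUP 1 as the highest grade in the other pathway, and no ISUP ≥2 in any biopsy.

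The same edit is the place to reconcile the lists of target conditions: section 10.2 has ISUP ≥1 where sections 2 and 8.1.2 have ISUP ≥2 with cribriform growth and/or intraductal carcinoma.

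The cost is a few sentences of text. No new data are needed and no stated objective is lost.
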